8.4.3 REPORTING UNANTICIPATED PROBLEMS TO PARTICIPANTS

Not applicable.

9 STATISTICAL CONSIDERATIONS

9.1 STATISTICAL HYPOTHESES

- Primary Efficacy Endpoint(s):

Phase 1:

The primary objectives are to assess safety and determine the recommended Phase II dose cabozantinib in combination with the standard of care, pembrolizumab. There are no primary efficacy endpoints for Phase I.

Phase 2:

The primary objective is to determine whether treatment with combination cabozantinib and pembrolizumab will increase the objective response rate (ORR) in patients with advanced melanoma compared to historic estimates for patients treated with pembrolizumab monotherapy. Historic ORR in patients treated with pembrolizumab monotherapy is reported to be approximately 35% [N Engl J Med. 2015 Jun 25;372(26):2521-32]. We anticipate the addition of cabozantinib will increase the ORR to 55%. In statistical terms, we are testing the null hypothesis $H_0: \text{ORR} \leq 35\%$ versus the alternative hypothesis $H_1: \text{ORR} \geq 55\%$.

- Secondary Efficacy Endpoint(s):

There are no formal and testable hypotheses for secondary endpoints.

9.2 SAMPLE SIZE DETERMINATION

Phase 1:

Phase I will utilize a standard 3+3 dose escalation design. A minimum of 6 and a maximum of 18 evaluable patients are required.

Phase 2:

When testing the null hypothesis that the $\text{ORR} \leq 35\%$ versus the alternative hypothesis that the $\text{ORR} \geq 55\%$, a sample size of 44 evaluable patients will ensure 80% power to detect a 20% absolute increase in ORR using an optimal Simon's two-stage design (Simon, 1989). Power estimates are based on an alpha = 0.05.

Based on historical trends our institution, the anticipated accrual rate is 2-3 patients per month.

9.3 POPULATIONS FOR ANALYSES

The safety population will include all enrolled patients who receive at least 1 dose of both cabozantinib and pembrolizumab. The safety population will be the analysis population for the safety analyses.

The modified intention-to-treat (mITT) population will comprise all patients who receive at least 1 dose of both pembrolizumab and cabozantinib, and who have baseline and at least 1 post-baseline imaging assessment. The mITT is the analysis population for the efficacy analysis.

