1.3 STUDY CALENDAR

Assessments	Screening 28-day window up to Day 1 of treatment ¹	Day 1 of Every ODD Cycles (1, 3, 5...) +/- 5 days	Day 1 of every EVEN cycle Cycles (2, 4, 6...) +/- 5 days	END of Treatment Visit ²	Follow Up ³ (every 3M from EOT Visit
Informed Consent ⁴	X				
Inclusion/Exclusion Criteria	X				
Medical History/ Prior Treatment ⁵	X				
Concomitant medications	X	X	X	X	
Physical Exam	X	X	X	X	
Performance Status (ECOG or KPS)	X	X	X	X	
Vital signs/Weight/Height ⁶	X	X	X	X	
Drug Toxicity Assessment ⁷	X	X	X	X	
Baseline daily stool count	X				
ECG ⁸	X ⁹	EVERY 12 weeks (Pre- Cycle 5, 9, 13, ...)		X	
ECHO- 2D/MUGA	X				
Pregnancy test ¹⁰	X				
CBC with Differential ¹¹	X	X	X	X	
Chemistries ¹²	X	X	X	X	
PT/INR and PTT ¹³	X			X	
Urinalysis and UPC	X	X	X	X	
Thyroid Function Tests ¹⁴	X		X	X	
Amylase, Lipase	X	Every 12 weeks (Pre-Cycle 5, 9, 13...)		X	
Hepatitis B and C ¹⁵	X				
Tumor Imaging- CT Chest/Abdomen/Pelvis ¹⁶	X	Every 12 weeks (Pre- Cycle 5, 9, 13...)		X	
Brain MRI ¹⁷	X				
Pill Diary/Pill Count ¹⁸		X	X	X	
Research Blood ¹⁹ Phase II only	X	At week 7 (+/- 1 week) and progression			
Archival Tissue ²⁰ Phase II only	X				
Tissue Biopsy ²¹ Phase II Part 2 only	X	At week 7 (+/- 1 week) and progression			
Cabozantinib PO		Daily	Daily		
Pembrolizumab IV (30- minute infusion)		Day 1 of each Cycle			
Survival Status					X

¹ Routine laboratory tests for screening should be performed within 14 days of cycle 1.

² End of treatment visit will be completed 30 days (+/- 7 days) from date of last dose of study drug or before another treatment starts whichever occurs first.

³ Subjects will be followed for survival and progression post treatment every 3 months x 2 years, every 6 months x 3 years and yearly until death. Every 3 months from EOT visit.

⁴ Written consent must be obtained prior to performing any protocol specific procedure. Results of a test performed as part of routine clinical management are acceptable in –lieu of a screening test if performed within the specified time frame. (e.g., within 28 days period to Cycle 1 Day 1.)

⁵ Report complete medication history for 30 days prior to the screening visit. Medical history should include history of treatment for the primary diagnosis, including prior systemic, radiation treatment and surgical treatment and best response to prior systemic treatments. Date of last prior cancer treatment must be documented.

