4.3 JUSTIFICATION FOR DOSE

4.3.1 PHASE 1B:

The Dose Escalation Phase 1b part will utilize a "3+3" design for escalation. The study plan includes the evaluation of 3 planned dose levels of cabozantinib administered orally. A minimum of 6 and a maximum of 18 subjects will be enrolled in each dose escalation cohort in Phase 1b, starting at 40 mg daily. The Sponsor reserves the right to adjust the planned cabozantinib dose levels based on emerging study data (Note: This will be considered as a protocol amendment) The planned cabozantinib dose levels to be studied in the Dose Escalation Phase 1b are presented in table 1. If the MTD has not been identified at the highest planned dose level, the Sponsor reserves the right to consider additional dose levels, and this would require a protocol amendment.

Table 1: Planned Dose Levels of Cabozantinib and Pembrolizumab

Dose Level	Cabozantinib	Pembrolizumab
-1	20 mg	200 mg
0 (starting dose)	40 mg	200 mg
1	60 mg	200 mg

Pembrolizumab will be administered at a standard recommended (drug label) dosing of 200 mg intravenously once every 3 weeks.

DLTs are defined in Section 4.3.2 Part 1 Dose Escalation: Dose-Limiting Toxicities (DLTs). The DLT rate across all subjects enrolled within a cohort in phase 1 must be <33% to allow escalation to the next dose level in that Arm. *The DLT observation period is 21 DAYS from date of first dose of cabozantinib.*

At the start of any new cohort, there will be a waiting period of at least 1 week after the first dose of the 3rd subject before enrollment of additional subjects into the same cohort. If a subject withdraws from the study prior to completion of the DLT assessment period for a reason other than a DLT, a replacement subject will be enrolled in that cohort.

Dose escalation in Part 1 to the next dose level can only occur after a minimum of 3 subjects have completed their DLT observation period for the current dose level, and the DLT rate does not exceed 33%.

Prior to escalation to a new dose level, the Safety Review Committee (SRC) will meet to review the safety data from the current cohort in order to determine if dose escalation is warranted.

The following rules govern dose escalation in Phase 1b:

- If none of the initial 3 subjects at a dose level experiences a DLT, escalation to the next dose level may occur. However, the Sponsor reserves the right to enroll up to 12 subjects in a cohort in order to obtain additional safety information.

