5 STUDY POPULATION

5.1 INCLUSION CRITERIA

A patient must meet all of the following criteria to be eligible for enrollment (defined as receiving the first trial treatment) in the trial:

1. Histologically or cytologically confirmed unresectable in-transit (stage IIIc) or metastatic (stage IV) melanoma.
2. Must have at least 1 lesion that qualifies as a measurable (target) lesion per RECIST v1.1
3. Subjects must be willing to have blood draws for future biomarker testing as outlined in Section 11.9.
4. The subject has an ECOG performance score of ≤ 2 However; the phase 1b part will include only ECOG performance of 0-1 and life expectancy of >12 weeks
5. Aged 18 years and older.
6. The subject should not have received any treatment for advanced melanoma, EXCEPT, BRAF and/or MEK inhibitor. (2 week washout)
7. The subjects who have received adjuvant therapy including anti- PD-1 can be included in the study, if the last dose of the adjuvant treatment was ≥ 6 months prior to developing metastatic relapse.
8. The subject is capable of understanding and complying with the protocol requirements and has signed the informed consent document.
9. Female patients of childbearing potential must have a negative urine or serum pregnancy test within 72 hours prior to taking the first dose of study medication, if. If the urine test is positive or cannot be confirmed as negative, then a serum test is required which must be negative for the patient to enroll. Women of childbearing potential (WOCBP) must be willing to use 2 medically acceptable methods of contraceptive from Day 1 through 120 days after the last dose of trial treatment. The 2 medically acceptable birth control methods can be either 2 barrier methods or a barrier method plus a hormonal method to prevent pregnancy. The following are considered adequate barrier methods of contraception: diaphragm, condom (by the partner), copper intrauterine device, sponge, or spermicide as per local regulations or guidelines. Appropriate hormonal contraceptives will include any registered and marketed contraceptive agent that contains an estrogen and/or a progestational agent (including oral, subcutaneous, intrauterine, or intramuscular agents). Male patients of reproductive potential must agree to use an adequate method of contraception from Day 1 through 120 days after the last dose of trial treatment. Abstinence is acceptable if this is the usual lifestyle and preferred contraception for the patient.

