6.3.2 FORMULATION, APPEARANCE, PACKAGING, AND LABELING

The identities and instructions for administration, storage, and handling of cabozantinib and pembrolizumab are described below. Both Cabozantinib and pembrolizumab are considered as, and referred to as, trial drug(s) or trial treatment in this protocol.

Cabozantinib: Chemical Name: *N*-(4-[(6,7-dimethoxyquinolin-4-yl)oxy]phenyl)-*N'*-(4-fluorophenyl)cyclopropane-1,1- dicarboxamide, (2S)-hydroxybutanedioate

Cabozantinib Tablets (XL184): Exelixis will provide investigator with adequate supplies of cabozantinib, which will be supplied as freebase 60-mg, and 20-mg yellow film-coated tablets. The 60-mg tablets are oval, and the 20-mg tablets are round. See Exelixis Study Pharmacy Manual.

Schedule, route of administration and dose: Subjects will receive cabozantinib orally. The cabozantinib dosing will vary according to the dosing levels in phase 1b and the final decided dose for phase 2 part of the trial. In all subjects, dose reductions and delays to manage toxicity are allowed under the guidelines.

Pembrolizumab [Keytruda® (US)], (commercially available) a humanized monoclonal antibody against the PD-1 protein, has been developed by Merck & Co for the treatment of cancer. Pembrolizumab may be supplied in 2 different formulations:

Pembrolizumab injection is supplied as a sterile, preservative-free, clear to slightly opalescent, colorless to slightly yellow solution that requires dilution for intravenous infusion. Each vial contains 100 mg of pembrolizumab in 4 mL of solution. Each 1 mL of solution contains 25 mg of pembrolizumab and is formulated in: L-histidine (1.55 mg), polysorbate 80 (0.2 mg), sucrose (70 mg), and water for injection, USP.

OR

- Pembrolizumab powder for solution for injection is a sterile, non-pyrogenic lyophilized powder for intravenous infusion supplied in single-use glass vial

containing 50 mg of pembrolizumab. The product is preservative-free, white to off-white powder, and free from visible foreign matter.

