
Grades 3 or 4 Grade 3: Prolonged (i.e., not rapidly responsive to symptomatic medication and/or brief interruption of infusion); recurrence of symptoms following initial improvement; hospitalization indicated for other clinical sequelae (e.g., renal impairment, pulmonary infiltrates)
 
Grade 4: Life-threatening; pressor or ventilatory support indicated
	
Stop Infusion. Additional appropriate medical therapy may include but is not limited to: IV fluids Antihistamines NSAIDS Acetaminophen Narcotics Oxygen Pressors Corticosteroids Epinephrine Increase monitoring of vital signs as medically indicated until the subject is deemed medically stable in the opinion of the investigator. Hospitalization may be indicated. Subject is permanently discontinued from further trial treatment administration.
	
No subsequent dosing

Appropriate resuscitation equipment should be available at the bedside and a physician readily available during the period of drug administration.
For Further information, please refer to the Common Terminology Criteria for Adverse Events v4.0 (CTCAE) at <http://ctep.cancer.gov>

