9.4.4 SAFETY ANALYSES

The incidence of treatment-emergent adverse events will be summarized by system organ class and/or preferred term, type of adverse event, severity (based on NCI CTCAE v4.03 grades), and relation to study treatment using the safety population. The most severe grade per patient will be reported. Elapsed days of toxicity will be summarized with descriptive statistics. Adverse events leading to premature discontinuation from the study intervention and serious treatment-emergent adverse events will be presented in tabular form. Changes in laboratory values and vital signs will be summarized with descriptive statistics. The incidence of concomitant medications will be summarized.

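### The safety population requires a dose of both drugs, so an enrolled patient who never receives the second drug, possibly because of toxicity, drops out of the adverse-event tables

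*Combined protocol and SAP*

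**What the plan says.** Section 9.3 defines the set: "The safety population will include all enrolled patients who receive at least 1 dose of both cabozantinib and pembrolizumab". It then assigns its use: "The safety population will be the analysis population for the safety analyses". Section 9.4.4 summarises adverse events by type, severity and "relation to study treatment using the safety population". It also calls for tables of serious events and of events that led to stopping the study intervention early. No other safety set is named, and Section 9.4.8 says that individual participant data will not be listed.

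Three other places decide who can fall outside the set:

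- Section 5.1 speaks of patients "eligible for enrollment (defined as receiving the first trial treatment) in the trial".
- Section 6.3.2 says: "Both Cabozantinib and pembrolizumab are considered as, and referred to as, trial drug(s) or trial treatment in this protocol".
- Section 6.6.2, Table 10, says of Grade 3 and 4 pembrolizumab infusion reactions: "Subject is permanently discontinued from further trial treatment administration".

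The study calendar (Section 1.3) places pembrolizumab on "Day 1 of each Cycle" and cabozantinib daily. It does not say which comes first on the opening day.

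**The concern.** A safety set normally holds everyone exposed to any study drug, so that no patient can leave it because of what the drug did. Here entry depends on reaching a second event, the first dose of the other drug, and an acute harm from the first drug is a reason not to reach it. The patients at risk of omission therefore include those whose treatment ended on the first day because of toxicity. They belong in the tables of serious events and of events leading to discontinuation, and Section 3 makes describing the safety profile a stated Phase 1 objective. With no any-dose set and no individual listings, the planned outputs have no other place where such an event would appear.

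**Working it through.** **Step 1. Can a patient be enrolled but outside the safety population?** Enrollment occurs at the first trial treatment (5.1), and each drug is a trial treatment (6.3.2). One dose of either drug therefore enrols the patient, while 9.3 asks for a dose of both. The gap is exactly the patients who receive one drug and never the other. A patient who is harmed by the first drug, recovers and later takes the second is included.

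**Step 2. Can toxicity put a patient there?** Yes. Under Table 10 a Grade 3 or 4 reaction at the first infusion ends trial treatment. If no cabozantinib has been taken, the both-drug condition can never be met. The reverse order (a tablet, an event, no infusion) has the same result. The calendar fixes no same-day order, and Section 6.3.4 requires cabozantinib to be taken fasting, so simultaneous first doses cannot be presumed.

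**Step 3. How many patients?** Inputs: 6 severe or life-threatening infusion reactions in 2799 pembrolizumab patients (2.3.1.2); at most 18 evaluable patients in Phase 1 and 44 in Phase 2 (9.2).

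- Reproducing the protocol's rate: 6/2799 = 0.21%, which it rounds to 0.2%.
- Patients: 18 + 44 = 62.
- Expected count: 62 × 0.002 = 0.12 (0.13 with the unrounded rate).
- Chance of at least one: 1 − 0.998^62 = about 12%.

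These are upper figures for this route, because the 0.2% is not limited to first infusions or to infusions given before any cabozantinib. The documents give no rate for the reverse route.

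**Step 4. What does an exclusion do to a table?** The documents give no count of one-drug patients, so this is an illustration under assumption: N = 44 treated in Phase 2, k of them given one drug only and each with the event, and x events among the rest. The both-drug rate is x/(N − k) and the any-dose rate is (x + k)/N.

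| k | x | Both-drug set | Any-dose set |
|---|---|---|---|
| 1 | 0 | 0/43 = 0% | 1/44 = 2.3% |
| 1 | 2 | 2/43 = 4.7% | 3/44 = 6.8% |
| 3 | 0 | 0/41 = 0% | 3/44 = 6.8% |
| 3 | 2 | 2/41 = 4.9% | 5/44 = 11.4% |

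The difference is k(N − k − x)/[N(N − k)], which is never negative. When the event causes the exclusion, the both-drug rate cannot be the higher one.

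**Step 5. When the excluded patient had no event.** With x = 2 and k = 1, the both-drug rate is 2/43 = 4.7% and the any-dose rate is 2/44 = 4.5%. The distortion is slight and runs the other way.

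**Step 6. Does the change touch the Phase 2 design?** No. The efficacy population has its own definition in 9.3 and does not refer to the safety population. The two-stage rule (stop at 5 or fewer responders of 14; reject at 21 or more of 44) gives exact alpha 0.0458 at 35% and power 0.8001 at 55% under either safety definition.

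**The case against.** The best defence is that the stated aim is the safety of the combination, and a both-drug set matches that aim. Both drugs are scheduled from Day 1 of Cycle 1, so hardly anyone will receive only one. This stands as to size and as a reason to keep a both-drug set. It does not justify making that set the only one, since the starting regimen is the combination and harm on the way to the second drug is part of its safety record.

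A reader might infer more than the documents support:

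- **That the event is lost to oversight.** Adverse events are recorded from consent (6.1.2.3, 11.6). Serious events go to the data and safety monitoring committee within 24 hours whether or not related (11, 11.6), and related ones go to the cabozantinib supplier (8.3.6, 11.7.1). None of this requires both drugs.
- **That dose escalation is distorted, with a cohort's 1 of 6 becoming 0 of 5.** Section 4.3.1 has its own denominator: "The DLT rate across all subjects enrolled within a cohort in phase 1 must be <33" per cent. Section 9.4.2 defines the recommended dose by DLTs without using the safety population, and 9.4.4 does not describe tables by dose cohort. The plan would report no such 0 of 5 as a DLT rate.
- **That the bias always runs downward.** A one-drug patient without an event, for example one who withdraws consent, raises the rate slightly when excluded (step 5).
- **That one omitted patient is necessarily 1 of 44.** Section 9.2 counts 44 evaluable patients, and a one-drug patient may not be among them.

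**Conclusion.** The point holds as one about the summary tables. Sections 9.3 and 9.4.4 together omit an enrolled patient who receives one drug and never the other, and the protocol contains a toxicity-driven route to that position. Where toxicity causes the omission, tabulated rates are too low, including those for serious events and for events leading to discontinuation. The number affected is probably zero to a few, with at most about 0.12 expected by the infusion-reaction route. That figure assumes that the 0.2% for pembrolizumab carries over to the combination and that about 62 patients are treated. Replacement patients would raise it by 0.002 each. Collection of events, serious-event reporting and dose-escalation decisions are not affected. This is a free improvement, not a threat to the trial's conclusions.

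**What to change.** Replace the first sentence of Section 9.3 with a definition on these lines: *the safety population comprises every enrolled patient given any amount of cabozantinib or of pembrolizumab.* The words *any amount* also settle whether a partly delivered infusion counts as a dose, which the present text leaves open. Footnote in the 9.4.4 tables any patient who received only one drug, and state which. If a description of patients exposed to the combination is wanted, keep the present both-drug set as a supplementary set.

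The cost is one sentence and a footnote. The adverse-event data are already collected from consent. Sample size, alpha and power are unchanged, and no dosing or management rule needs to change.

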A minimum of 3 subjects will be enrolled in each Cohort. The maximum allowed DLTs per cohort to allow subsequent dose escalation is 1 DLT observed in 6 subjects. The sponsor may also choose to enroll up to 6 subjects initially into a cohort. Dose escalation will proceed if no more than 1 DLT is observed in 6 subjects to the next dose level. The dose level 1 will be the maximum allowed dose.

If ≥ 2 of 6 subjects experience a DLT in any cohort, dose escalation will cease and the previous lower dose of cabozantinib may be designated the MTD and RP2D. If ≥ 2 of 6 patients experience a DLT in the Dose level 0, then a step cohort (Dose level -1) will be enrolled with cabozantinib administered daily at 20 mg daily and pembrolizumab 200 mg once every 3 weeks, as per the package label. However, the sponsor may also decide to investigate an additional lower or intermediate dose group(s) than have already been tested. In such a scenario, the protocol will be amended. Subjects will be enrolled and evaluated as described above for previous dose escalation cohorts except that staggered enrollment with a sentinel subject will not be required. Three to 6 subjects will be enrolled at the intermediate or lower dose and DLT assessments performed, with expansion to 6 subjects as required and applicable. A maximum of 0 DLTs in the first 3 subjects or 1 DLT in the first 6 subjects will define this dose as the MTD.

4.2.2 PHASE 2:

The phase 2 part of the study will be run in two stages. In the first stage, 14 subjects will be accrued. If there are 5 or fewer responses in these 14 subjects, the study will be stopped.

Otherwise, 30 additional subjects will be accrued for a total of 44 subjects. This study design will have a limited enrollment of subjects to the trial if the combination does not show a

signal of activity in advanced melanoma.

4.2.3 BLINDING:

Blinding will not be performed as this is an open-label trial.

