8 STUDY ASSESSMENTS AND PROCEDURES

8.1 EFFICACY ASSESSMENTS

The intention of the study design is to closely monitor patients with safety follow-up and disease assessments in the absence of disease progression or other study discontinuation criteria.

For the purposes of this study, patients should be re-evaluated after the first 12 weeks of treatment and then every 12 weeks. **In addition to a baseline scan, confirmatory scans will** also be obtained at least 4 weeks and no more than 14 weeks following initial documentation of partial or complete response.

Primary efficacy endpoint is best ORR defined as the proportion of all treated subjects whose best response at any time during the study following initiation of therapy is confirmed CR or confirmed PR. This will be assessed according to the RECIST v1.1.(Appendix A).

PFS, defined as the time between the first dose of study therapy and the earliest date of progression or death. Subjects who have neither progressed nor died will be censored at the last tumor assessment date for PFS. The endpoint ORR and PFS will be assessed according to the RECIST v 1.1 criteria.

Additional efficacy endpoints will include the disease control rate (DCR) defined as the percentage of patients achieving CR + PR + SD at any time during the study following initiation of therapy. This will be assessed according to RECIST v1.1 criteria. The duration of response (DOR), is defined as the time between the date that the criteria are first met for CR or PR or SD and the earliest date of progression or death.

OS, defined as the time between the first dose of study therapy and death (subjects who have not died will be censored at the most recent last-known-alive date), will also be analyzed.

The tumor assessment (TA) performed during screening will be used as a baseline for efficacy assessments. CT/MRI imaging of the chest and abdomen is required at Screening and at each TA, regardless of the location of known metastases. In addition, CT/MRI scans must be obtained of anatomic regions not covered by the chest and abdomen scans in subjects where there is clinical suspicion of deep soft tissue metastases (eg, lesions in the thigh). Such additional CT/MRIs will be required at Screening when deep soft tissue disease is known/suspected and must be consistently repeated at all TAs if a deep soft tissue lesion is identified during Screening.

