The same imaging modality must be used for all TAs, unless contraindicated. Imaging-based evaluation is preferred to clinical examination. Helical (spiral) CT scans of the chest and abdomen is preferred. If not available, MRI can be used; however, a measurable lesion must not have the longest diameter smaller than 10 mm by MRI (10 mm on spiral CT). IV contrast should be used for all CT scans; if IV contrast is contraindicated, oral contrast maybe used, or MRI should be used at the Screening exam and at all TA time points. Subjects who develop contrast allergy after study enrollment must be followed by MRI for subsequent tumor measurements.

Sections should be contiguous, similarly sized and consistent from visit-to-visit. Section thickness must be based on institutional standards (e.g., from 5 to 8 mm, 10 mm cuts are not recommended). Chest x-rays and ultrasound are not acceptable methods to measure disease. Response and progression of disease must be documented by CT or MRI similar to the methods used at Screening.

If bone lesions are identified at any time during the study, additional imaging studies of the lesion(s) must be performed to confirm the malignant nature of the new findings on the bone scan. If an abnormal bone scan is observed at any time point throughout the study, a repeat bone scan must be performed prior to the confirmation of a CR (e.g., the remaining metastatic lesions must have resolved. In case of new lesions such as pleural effusion, cytology must be performed to identify and confirm malignancy. Skin and soft tissue lesions will be captured as non-measurable lesions through physical examination only.

Any subject who develops an objective tumor response (CR or PR) should undergo a second scan for confirmation at least 4 weeks later (and no more than 14 weeks). For subjects with progression (PD) consider confirmatory scans at least 4 weeks (and no more than 14 weeks) from the prior scan in order to verify the reliability of the radiologic findings.

Definition of Measurable / Non-measurable Lesions

- -Measurable lesions are lesions that can be accurately measured in 2 perpendicular diameters, with at least one diameter > 20 mm and the other dimension > 10 mm on MRI, or 10 mm x 10 mm for spiral CT. The area will be defined as the sum of the largest diameter with its perpendicular.

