9.4.2 ANALYSIS OF THE PRIMARY EFFICACY ENDPOINT(S)

Phase I:

There are no primary efficacy endpoints for Phase I. The recommended Phase II dose is defined as the highest dose level for which at most 1 out of 6 patients experience a DLT.

Phase II:

The primary efficacy endpoint is ORR. ORR is defined as the proportion of patients with RECIST disease response (CR, PR). All patients that do not meet the criteria for an objective response by the analysis cutoff date will be considered non-responders.

Phase II is utilizing an optimal Simon's two-stage design. As such, 14 patients will be enrolled in the first stage. If 5 or fewer patients respond (CR or PR), the study will be terminated due to futility. Otherwise, an additional 30 patients will be enrolled in the second stage. As per the decision rules of the design, the null hypothesis will be rejected if at least 21 patients respond (CR or PR) out of the 44 total patients. The ORR and 95% exact confidence interval will be reported.

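### Section 9.3 drops treated patients who have no post-baseline scan, while section 8.1 defines the primary ORR over all treated subjects; following 9.3 can only push the reported ORR up

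*Combined protocol and SAP*

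**What the plan says.** Two sections give the primary endpoint different denominators.

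- Section 8.1 (Efficacy Assessments) has "best ORR defined as the proportion of all treated subjects whose best response at any time during the study" is a confirmed CR or PR. The denominator is everyone treated.
- Section 9.3 (Populations for Analyses) defines the mITT set as patients given at least one dose of both drugs "who have baseline and at least 1 post-baseline imaging assessment. The mITT is the analysis population for the efficacy analysis". The denominator is everyone scanned.

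Other sections bear on which one governs:

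- Section 9.4.2: "All patients that do not meet the criteria for an objective response by the analysis cutoff date will be considered non-responders". It names no population. It tests for at least 21 responders among 44 total patients.
- Section 9.4.3 names the mITT set for DCR, PFS and OS.
- Section 8.1 on evidence of response: "Response and progression of disease must be documented by CT or MRI similar to the methods used at Screening".
- Section 5.1 treats a patient as "eligible for enrollment (defined as receiving the first trial treatment) in the trial". Section 4.2.2 says "In the first stage, 14 subjects will be accrued", and 9.4.2 says "Otherwise, an additional 30 patients will be enrolled in the second stage". Together these point to 14 + 30 = 44 treated patients.
- Section 9.2 alone uses another label: "a sample size of 44 evaluable patients will ensure 80% power". The term is not defined for Phase 2.
- The only replacement rule, in section 4.3.1, concerns the Phase 1b DLT period.
- Appendix A, a generic RECIST reference, keeps all eligible patients in the main response analysis and counts early deaths and unknowns as failures. It leaves the precise failure categories to the protocol.

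**The concern.** A statistician following 9.3 would drop an unscanned patient. One following 8.1 would count that patient as a failure. Both could claim to follow the plan, and in an open-label single-arm trial that choice should not stay open once outcomes are visible.

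The non-responder rule in 9.4.2 does not settle it, because it can be read as applying only to patients left in the set after 9.3.

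The exclusion is not neutral. The first scheduled post-baseline scan is at week 12, so those most exposed are patients who die or leave early. For OS the scan condition has no purpose, yet a death before any scan would be left out. For PFS, section 9.4.3 counts death as an event from treatment start, while 9.3 removes deaths that precede the first scan.

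**Working it through.** **1. The plan's own design.** Inputs from 9.1, 9.2 and 9.4.2: null ORR 35%, alternative 55%, alpha 0.05 (taken as one-sided), stop at 5 or fewer responders in 14, reject at 21 or more of 44. The exact rejection probability is

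P(reject | p) = Σ over x = 6 to 14 of P(X1 = x) × P(X2 ≥ 21 − x), with X1 ~ Bin(14, p) and X2 ~ Bin(30, p).

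This gives 0.0458 at p = 0.35 and 0.8001 at p = 0.55. The stated design reproduces.

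**2. Direction.** With R responders among N treated and m unscanned, 8.1 reports R/N and 9.3 reports R/(N − m). Unscanned patients cannot be in R, so R/(N − m) > R/N whenever R > 0 and m > 0. With f = m/N, the ORR is multiplied by 1/(1 − f). DCR also rests on RECIST imaging and is multiplied by the same factor.

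**3. Size in the reported ORR** (Clopper-Pearson 95% limits; m is assumed):

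| Responders | Denominator | ORR | 95% CI |
|---|---|---|---|
| 20 | 44 (none dropped) | 45.5% | 30.4 to 61.2 |
| 20 | 42 (2 dropped) | 47.6% | 32.0 to 63.6 |
| 21 | 44 (none dropped) | 47.7% | 32.5 to 63.3 |
| 21 | 42 (2 dropped) | 50.0% | 34.2 to 65.8 |
| 21 | 41 (3 dropped) | 51.2% | 35.1 to 67.1 |

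At 21 responders the lower limit passes 35% only once 3 of 44 are dropped. The interval is not the decision rule: with nobody dropped, its lower limit is below 35% at 21 responders (32.5%) and at 22 (34.6%).

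**4. How likely any exclusion is.** The documents give no unscanned share, so f is assumed and the count is Bin(44, f):

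| f | P(at least 1) | P(at least 3) |
|---|---|---|
| 2% | 0.59 | 0.06 |
| 5% | 0.90 | 0.38 |
| 10% | 0.99 | 0.83 |

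**5. Effect on the test, by reading of the 44.**

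*44 treated patients, fixed cutoffs.* Dropping non-responders leaves the response counts as they were. Type I error is 0.0458 at any f.

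*44 scanned patients, unscanned ones replaced.* The rate among scanned patients is p/(1 − f), where p is the all-treated rate. Section 2.3.2.2 reports 91 of 277 (32.9%) and 94 of 279 (33.7%) responders in the two pembrolizumab arms of the randomized study, so those rates are shown beside the design null:

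| f | p = 35% | p = 91/277 | p = 94/279 |
|---|---|---|---|
| 2% | 0.056 | 0.029 | 0.038 |
| 5% | 0.076 | 0.041 | 0.052 |
| 10% | 0.123 | 0.069 | 0.088 |

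**6. Power if 55% was meant for scanned patients only.** With 44 treated, the all-treated rate is 0.55(1 − f). Power is 0.76 at 2% unscanned, 0.70 at 5% and 0.58 at 10%, against 0.80.

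**The case against.** The strongest reply is that section 9.4.2 already implies the right answer. It enrolls 14 + 30, calls every patient without a response a non-responder, tests 21 of 44 total patients, and then says the ORR and its interval will be reported. Unlike 9.4.3, it does not name the mITT set. On that reading only one general sentence in 9.3 is out of line. The effect is also modest: one unscanned patient moves 21/44 = 47.7% to 21/43 = 48.8%, about 1.1 points in an interval about 31 points wide. The secondary endpoints are descriptive. The inflated error rates need a replacement practice that no section provides for.

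Most of this stands as a limit on size. It supports 44 treated patients as the better reading, and the type I figures in step 5 are a reason to close off the other reading, not evidence of a faulty test. It does not remove the conflict, because 9.3 expressly assigns the efficacy analysis to the mITT set and 9.4.2 does not override it.

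The number of unscanned patients may be small. Section 1.2 requires a life expectancy above 12 weeks, the study calendar includes an end-of-treatment scan, 7.2 continues scans after stopping without progression, and 8.1 allows extra scans on suspected progression.

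Three narrower points:

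- Appendix A accepts superficial lesions as clinically measurable, but 8.1 classes skin and soft tissue lesions as non-measurable and requires CT or MRI for response.
- Re-deriving the cutoff for a smaller N would also change the error rate. The plan does not provide for this, and stating fixed cutoffs rules it out.
- The one-way direction belongs to the scan condition. The separate requirement of a dose of both drugs could in principle remove a responder.

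**Conclusion.** The concern holds: the text is wrong as written. Sections 8.1 and 9.3 give different denominators for the primary ORR, and following 9.3 raises the reported ORR and DCR by a factor of 1/(1 − f) whenever a treated patient has no scan and there is a response or disease control to count. PFS and OS would describe only patients who reached a scan.

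Under the best-supported reading the go/no-go decision is unaffected, so the damage is to the estimate and its interval: about 2 points at 20 responders with 2 unscanned. That size rests on an assumed unscanned count. Confidence is high for the textual conflict and the direction. This should be fixed, but it does not invalidate the two-stage test.

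**What to change.** - **9.3:** make all Phase 2 patients who receive any trial treatment the primary efficacy population, in line with 8.1 and the enrollment definition in 5.1. This also drops the both-drugs condition for efficacy. Keep the mITT set as a labelled sensitivity analysis.
- **9.4.2:** name that population beside the existing non-responder rule, and count patients with no post-baseline scan as non-responders at both Simon stages.
- **9.4.3:** count them as failures for DCR and include them in PFS and OS, with death before the first scan as a PFS event.
- **9.2:** replace 'evaluable' for Phase 2, so that 14 and 44 are treated patients who are not replaced, the cutoffs (more than 5, at least 21) are fixed, and 55% is stated as an all-treated rate.

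**Cost:** a wording amendment, which needs Exelixis and IRB approval under the Statement of Compliance, and a slightly lower reported ORR if anyone is unscanned. No extra patients are needed if 55% is an all-treated rate. If it was meant for scanned patients only, the 80% power claim should be restated using the figures in step 6 of the working.
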